## 5.5 Trial Outcomes

Clinical data and the survey scores from clinicians, patients, and technologists obtained directly after using the Brevera Breast Biopsy System and standard-of-care breast biopsy procedures will be compared for overall preference and performance of the biopsy systems.

# 5.6 Schedule of Assessment(s)

Clinicians, patients, and technologists will be asked about their experience as it directly relates to the procedure that they underwent or performed. Additionally, subjects will have data and procedure metrics will evaluated from the beginning of the procedure through their release from the outpatient treatment facility. Pathology results will be recorded following the procedure once they become available.

Table 2 - Schedule of Assessments
-----------------------------------

Assessment	Baseline	Procedure
Informed Consent	Х	
Medical History*	Х	
Physical Assessment*	Х	Х
Adverse Event Evaluation		Х
Procedure*		Х
Questionnaires**		Х

\* Per standard-of-care

## 5.7 Subjects

This trial will recruit up to 525 females 18 years of age or older with suspicious findings on mammographic screening or diagnostic exam who are sent for biopsy. The overall recruitment numbers include the five (5) run in cases per radiologist at each site.

## 5.7.1 Inclusion Criteria

- 1) Female aged 18 years of age or older
- 2) Subject has at least one breast imaging finding requiring biopsy for which images are available

\*\* To be completed by clinicians, patients, and technologists

3) Subject is able to understand, read and sign the trial specific informed consent form after the nature of the trial has been fully explained to her

#### 5.7.2 Exclusion Criteria

- 1) Patients who, based on the physician's judgement, may be at increased risk or develop complications associated with core removal or biopsy.
- 2) Patients receiving anticoagulant therapy or may have bleeding disorders which may put the patient at increased risk of procedural complications based upon physicians judgement.

## 5.7.3 Informed Consent & Enrollment Procedures

Although the device in this trial has received FDA clearance for commercial use, informed consent shall be obtained in writing from the subject or their legally authorized representative and the process shall be documented before any procedure specific to the clinical trial is applied to the subject, in order to collect procedural specific data.

The general process for obtaining informed consent shall:

- ensure that the Principal Investigator or his/her authorized designee conducts the informed consent process;
- include all aspects of the clinical trial that are relevant to the subject's decision to participate throughout the clinical trial;
- avoid any coercion or undue improper influence on, or inducement of, the subject to participate;
- not waive or appear to waive the subject's legal rights;
- use native non-technical language that is understandable to the subject;
- provide time for the subject to read and understand the informed consent form and to consider participation in the clinical trial;
- include personally dated signatures of the subject and the principal investigator or an authorized designee responsible for conducting the informed consent process;
- provide the subject with a copy of the signed and dated informed consent form and any other written information; and,
- ensure the patient is aware that the de-identified case report forms and images are being sent to Hologic, in the United States.

Upon signing the Informed Consent Form, the subject is considered enrolled in the trial.

# 5.7.4 Subject Withdrawal/Discontinuation

A subject will be discontinued from participation in the trial if:

- The Investigator feels that the subject can no longer fully comply with the requirements of the trial or if any of the trial procedures would not be in the best interest of the subject.
- The subject wishes to withdrawn their consent for participation in the trial.

# 5.8 Expected Trial Duration

Study Start:Q3/2017Enrollment Completion:Q1/2018Final Report:Q2/2018

#### 6. TRIAL PROCEDURES

The trial will collect de-identified case report form data and patient images from biopsy procedures. This will include collection of images from the prior exam leading up to the breast biopsy procedure. The biopsy procedures will be done consistent with current clinician direction/standard-of-care.

Prior to use of the new Brevera Breast Biopsy System, normal applications training will take place in order to train the users on new features and quality control testing.

Patients will be enrolled using a block randomization. Each clinician will complete ten (10) patients in block 1 and ten (10) patients in block 2. (Blocks will be defined as either the Standard-of-care biopsy system or the Brevera Biopsy system). A clinician must complete block 1 before moving on to block 2.

[figure not shown]
Clinical data will be collected on the procedure within each block by patient procedure. The procedures will collect data related to time of procedure, number of cores collected, post biopsy results and survey data on the system.

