# Figure Legend

- 1. Biopsy device
- Remote control for mode control and arming or firing the biopsy device
- 3. Technologist display
- 4. Imaging display
- 5. Vacuum line assembly and suction canister
- 6. Tissue filter assembly
- 7. Tissue filter drawer
- 8. Footswitch
- 9. Power cord

The user interface for data entry, patient selection, and image acquisition and review is on the Imaging display. The user interface for controlling the modes of the biopsy device are buttons on the Technologist display and on the remote control device. The user interface for arming and firing the biopsy device is on the remote control device. The user rotates the aperture on the biopsy device with the thumbwheel on the disposable biopsy needle. The user adjusts the size of the aperture on the biopsy device by assembling the introducer in one of two preset positions along the needle shaft.

The control devices for this study will be the current devices already used for breast biopsy procedures.

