## 8. STATISTICAL CONSIDERATIONS

7 clinical trial sites each with 3 radiologists performing 20 biopsies (10 with local standard-of-care, and 10 with the Brevera Breast Biopsy System, as per randomization procedure) results in a total of 420 subjects enrolled in phase 2. This sample size achieves approximately 80% power to detect a difference in mean procedure time of 3 minutes between the Brevera and standard of care biopsy systems assuming a standard deviation of 12 minutes in procedure time and an intraclass correlation of 0.150 at a standard significance level of alpha=0.05. Mixed effects regression will be utilized to assess the impact of the biopsy device (e.g., Brevera or local standard-of-care) on total procedure time, post-biopsy complication rates and differences in discordant biopsies. For these analyses, biopsy device type, subject physical habitus and lesion location (i.e., "near the chest wall or axilla?" yes/no) will be considered fixed effects, and site and radiologist will be considered random effects. Total tissue acquisition by number of cores, total acquired sample mass, and total tissue utilized by pathology for diagnosis will be compared between the Brevera system and local standard-of-care using Analysis of Variance (ANOVA) testing. Lastly, sub-analyses will be performed to look at specific comparisons between the Brevera system and other biopsy systems if multiple sites utilize the same biopsy system as their standard-of-care device.

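### Each radiologist uses the two devices in separate ten-case blocks, but the procedure-time model, on its natural reading, has no term for device differences that vary between radiologists or sites, so its 5% error rate rests on an unstated assumption

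*Combined protocol and SAP*

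**What the plan says.** Section 6 (Trial Procedures) fixes the case sequence for each radiologist in Phase 2: "Each clinician will complete ten (10) patients in block 1 and ten (10) patients in block 2". It explains that "Blocks will be defined as either the Standard-of-care biopsy system or the Brevera Biopsy system", and adds "A clinician must complete block 1 before moving on to block 2". Each radiologist therefore contributes one run of ten Brevera cases and one run of ten control cases.

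Section 8 (Statistical Considerations) analyses procedure time, the primary endpoint, by mixed effects regression. The fixed effects are device, body habitus and lesion location; "site and radiologist will be considered random effects". It names no radiologist-by-device, site-by-device or block term. On sample size it says: "This sample size achieves approximately 80% power to detect a difference in mean procedure time of 3 minutes", "assuming a standard deviation of 12 minutes in procedure time and an intraclass correlation of 0.150".

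On the comparator, the text after the figure legend in Section 2.2 says: "The control devices for this study will be the current devices already used for breast biopsy procedures". Section 8 plans comparisons with particular systems only "if multiple sites utilize the same biopsy system as their standard-of-care device", so it allows for control systems that differ between sites.

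**The concern.** Cases within a block share more than the device. They fall in one stretch of time and may share staffing, case mix and the radiologist's current pace. They also share that radiologist's own gain or loss from changing device. A random radiologist intercept removes what is common to all 20 of a radiologist's cases. It does not remove what is common to only one of the two blocks.

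If such variation exists, the device effect is replicated over 21 radiologists rather than over 420 independent cases. A model that omits the term computes too small a standard error for the device effect. The consequence is a type I error above 5% on the primary endpoint, in a trial whose results are meant to support marketing claims and publications (Section 5.4.2).

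**Working it through.** **Inputs from Section 8.** 7 sites × 3 radiologists = 21 radiologists; 10 cases per device each, so 210 per device; difference 3 minutes; SD 12 (variance 144); intraclass correlation 0.150; alpha 0.05. Two-sided testing is assumed, because sidedness is not stated. The clustered variance is 0.15 × 144 = 21.6 and the residual variance is 0.85 × 144 = 122.4.

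**Step 1: reproduce the stated power.** With a radiologist intercept only, the intercept cancels in the device contrast:

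SE = √(2 × 122.4 / 210) = 1.080; 3 / 1.080 = 2.779; power = Φ(2.779 − 1.960) = 79.3%.

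This matches the stated figure. Ignoring the clustering gives 72.6%. A design effect of 1 + 9 × 0.15 = 2.35 gives 38.6%. The stated power therefore fits the model without a device-varying term.

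**Step 2: let the two blocks differ.** Let v be the variance of a radiologist's block effect. The documents give no value, so v is taken as an assumed share of 21.6.

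- True SE = √(2 × (122.4/10 + v) / 21).
- The planned model pools 20 df of radiologist-by-device variation with 378 df of within-block variation (42 blocks × 9): MS = [20 × (122.4 + 10v) + 378 × 122.4] / 398. Its SE is √(2 × MS / 210).
- Planned type I error = 2 × [1 − Φ(1.96 × planned SE / true SE)].
- Planned rejection rate at 3 minutes = Φ((3 − 1.96 × planned SE) / true SE); the opposite tail is negligible.
- Valid-test power comes from the noncentral t with 20 df and noncentrality 3 / true SE.

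Example at a 10% share: v = 2.16; true SE = √(2 × 14.40 / 21) = 1.171; MS = 123.49 and planned SE = 1.084; ratio 0.926; type I error = 2 × [1 − Φ(1.815)] = 7.0%.

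| Share of 21.6 (assumed) | Block SD, min | True SE | Planned SE | Planned type I error | Planned rejection rate at 3 min | Power, t on 20 df |
|---|---|---|---|---|---|---|
| 0% | 0 | 1.080 | 1.080 | 5.0% | 79% | 75% |
| 5% | 1.0 | 1.126 | 1.082 | 6.0% | 78% | 72% |
| 10% | 1.5 | 1.171 | 1.084 | 7.0% | 77% | 68% |
| 20% | 2.1 | 1.256 | 1.089 | 8.9% | 75% | 62% |

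The drop from 79% to 75% in the first row is the price of estimating the term on 20 df. It is not a fault in the plan.

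**Step 3: variation shared by a site's radiologists.** If the device difference varies between sites with SD S (assumed), the variance of the estimate is 2 × 122.4/210 + S²/7. Results by simulation (type I error) and noncentral t (site-level power):

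| S, min (assumed) | Type I error, planned | Type I error, radiologist-level (20 df) | Power at 3 min, site-level (6 df) |
|---|---|---|---|
| 0 | 5.0% | 5.0% | 64% |
| 1 | 6.4% | just under 6% | 59% |
| 2 | about 11% | about 8% | 48% |

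The site-level test holds 5% throughout.

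**The case against.** Four points can be made for the plan.

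- **The harm is conditional.** The documents give no block variance. At zero variance the planned analysis is valid, and the range above has no anchor in the protocol. This stands, and it limits the strength of the point.
- **Section 8 is a summary.** Naming random effects does not strictly exclude a random device slope. This also stands. But if a slope was intended, the test has about 75% power before any covariate gain, so the text needs clarifying either way.
- **The plan already reduces block variation.** Five run-in cases per radiologist (Section 5.4.1) and the habitus and lesion-location covariates remove some of it. They do not replace the term.
- **The remedy does not match the evidence.** The only reason in the documents to expect variation is that control systems may differ between sites. That acts at site level, where a radiologist-level term helps only in part (Step 3). This stands, and it is why the fix includes a site-level analysis.

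A reader might infer that the stated 80% is a miscalculation, or that the planned test collapses. The documents do not support that: the figure reproduces, and the planned test still rejects 78% and 77% of the time at 5% and 10% shares. The fault there is its error rate. A reader might also infer that device is confounded with order across the whole trial. The documents do not support that either: allocation is set before start-up (Section 5.4.2), and the figures that would show the order are not available.

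**Conclusion.** The point holds as an inexpensive improvement that should be made, with medium confidence. The stated power is arithmetically right, but the planned test is exact only if the device difference is the same for every radiologist and site, and the plan does not say so. Any positive variance makes the primary test anti-conservative: about 6, 7 or 9% instead of 5% at shares of 5, 10 or 20%. A valid radiologist-level test then has 72, 68 or 62% power.

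These figures rest on two-sided testing, full enrolment with no missing procedure times, no gain from covariates, and an assumed block variance. They show how sensitive the test is and do not predict this trial's actual error rate. A very small variance would change little.

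**What to change.** Change the wording of Section 8 only; the conduct of the blocks and the sample size stay as they are.

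1. For procedure time, add a radiologist-by-device (block) random effect. Name one primary test: the covariate-adjusted device effect against the between-radiologist variation in block differences, with t on 20 df.
2. Because control systems may differ between sites, add a site-by-device random effect or a site-level test as a sensitivity analysis. Say that the primary test corrects only part of any site-shared variation (type I error about 8% at an assumed 2-minute between-site SD), and that the 6-df site-level test has only about 64% power even at zero variance.
3. State the common-device-effect assumption behind the 80%. Report power for the named test as 75, 72, 68 and 62% at shares of 0, 5, 10 and 20%.

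**Cost.** About four points of stated power (79% to 75%) even if there is no block variance. Covariates may recover some of this: if they explained 10% of the residual variance (assumed), 20-df power at zero block variance would be about 80%. The enrolment cap of 525 is already filled by 21 radiologists × 25 cases including run-in, so the sponsor would accept the lower stated power.

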# 6.1 Safety/Device Assessment

## 6.1.1 Adverse Events

An adverse event (AE) is any untoward medical occurrence, unintended disease or injury or any untoward clinical signs (including an abnormal laboratory finding) in subjects, users or other persons whether or not related to the trial medical device. Each AE is considered either anticipated or unanticipated as described below. The site is required to report all device and procedure related AEs that occur in the trial following treatment to the study sponsor, Hologic, Inc. See Figure 3 below for the AE reporting flowchart.

Figure 3: AE Reporting Flow Chart:

The time-period for the assessment of the occurrence of an AE will begin at the time of consent until the subject has been discharged and will be based on changes in the subject's physical examination, laboratory results and/or signs and symptoms. AEs are to be monitored until they are resolved or clearly determined to be a stable or chronic condition or due to an undercurrent illness. Medical care will be provided, as defined in the informed consent, for any AE related to trial participation.

There are two types of AEs: anticipated or unanticipated. Subjects who experience any untoward aftereffects are instructed to contact their Investigator or coordinator immediately. The Investigator must determine both the intensity of the AE and the event's relationship to the breast biopsy system.

**AE Severity Classification**: Severity will be defined according to the following criteria:

- Mild Awareness of event, but easily tolerated
- Moderate Discomfort enough to cause some interference with activities of daily living (ADL)
- Severe Incapacitating, with an inability to perform activities of daily living (ADL)

Life threatening events, events where the subject was at risk of death, are serious AEs and must be reported in accordance with the procedures and timelines in this protocol.

**AE Relationship Classification**: Relationship to trial product use will be determined as follows:

- **Not Related** relationship to the device or procedures can be excluded when:
  - The event is not a known side effect of the product category the device belongs to or of similar devices and procedures
  - The event has no temporal relationship with the use of the device or the procedures
  - The serious event does not follow a known response pattern to the medical device (if the response pattern is previously known) and is biologically implausible
  - The discontinuation of the medical device application or the reduction of the level of activation/exposure- when clinically feasible- and reintroduction of its use (or increase of the level of activation/exposure), does not impact the serious event
  - the event involves a body-site or an organ not expected to be affected by the device or procedure
  - the serious event can be attributed to another cause (e.g. an underlying or concurrent illness/ clinical condition, an effect or another device, drug, treatment or other risk factors)
  - the event does not depend on a false result given by the trial device used for diagnosis when applicable
  - o harms to the subject are not clearly due to use error
  - o in order to establish the non-relatedness, not all the criteria listed above might be met at the same time, depending on the type of device/ procedures and the serious event.
- **Unlikely** The relationship with the use of the device seems not relevant and/or the event can be reasonably explained by another cause, but additional information may be obtained.
- **Possible** The relationship with the use of the device is weak but cannot be ruled out completely. Alternative causes are also possible (e.g. an underlying or concurrent illness/ clinical condition/ or and an effect of another device, drug or treatment), Cases where relatedness cannot be assessed or no information has been obtained should also be classified as possible.
- **Probable** the relationship with the use of the trial device seems relevant and/or the event cannot reasonably be explained by another cause, but additional information may be obtained
- **Causal Relationship** the serious event is associated with the device or with the procedures beyond reasonable doubt when:
  - The event is a known side effect of the product category the device belongs to or of similar devices and procedures
  - The event has a temporal relationship with the device application/use or procedures
  - the event involves a body-site or organ that:
  - the device or procedures are applied to
  - the device or procedures have an effect on
  - the serious event follows a known response pattern to the medical device (if the response pattern is previously known)
- the discontinuation of the medical device application (or reduction of the level of activation/exposure) and reintroduction of its use (or increase of the level of activation/exposure), impact on the serious event (when clinically feasible)

- Other possible causes (e.g. an underlying or concurrent illness/ clinical condition or/and an
  effect of another device, drug or treatment) have been adequately ruled out
- Harm to the subject is due to error in use
- the event depends on a false result given by the device used for diagnosis, when applicable
- in order to establish the relatedness, not all the criteria listed above might be met at the same time, depending on the type of device/procedures and the serious event

**AE Outcome Classification**: Outcome of the event will be defined according to the following:

- Resolved The event is resolved and is no longer present
- Not resolved The event has not yet been resolved
- Resolved with sequelae The event has resolved, but with an after affect possibly due to disease, injury, treatment or procedure
- Fatal The event resulted in subject death

## 6.1.2 Serious Adverse Events (SAEs)

# A SAE is any adverse event that:

- Led to death
- led to a serious deterioration in health that either:
  - o resulted in a life threatening illness or injury, or
  - o resulted in a permanent impairment of a body structure or a body function, or
  - o required in-patient hospitalization or prolongation of existing hospitalization or
  - resulted in medical or surgical intervention to prevent life threatening illness or injury or permanent impairment to a body structure or body function
- led to fetal distress, fetal death or a congenital abnormality or birth defect

## 6.1.3 Adverse Device Effect

An AE, which in the judgment of the Investigator, results from use of the trial device.

# 6.1.4 Anticipated AEs/Adverse Device Effects

List of foreseeable AEs and anticipated adverse device effects, together with their likely incidence, mitigation, or treatment. These events are related to the biopsy procedure and not necessarily the devices being used for the trial.

Anticipated, procedure-related AEs may include, but are not limited to, the following:

- Bruising and swelling of the breast
- Infection or bleeding at the biopsy site
- Altered breast appearance, depending on how much tissue is removed and how your breast heals
- Excessive post procedural pain at the biopsy site

# 6.1.5 Unanticipated Adverse Device Effect

An Unanticipated Adverse Device Effect (UADE) is a serious adverse device effect, which by its nature, incidence, severity or outcome has not been identified, in the current version of the risk analysis report.

# 6.2 Reporting Procedures

## 6.2.1 Investigator Reporting

The Investigator at each participating center is ultimately responsible for reporting applicable AEs to Hologic. The information to be reported on the AE CRF and should include the start date of the AE, treatment, resolution, and assessment of both the seriousness and the relationship to the device and should be captured on the AE CRF. The Investigator should report all AEs to the IRB, as required.

If there is a device malfunction or other observation (deficiency), the Investigator should notify Hologic immediately via the normal complaint procedure for commercially available devices, indicate if the observation resulted in an AE, and indicate if complications are related to the device, procedure or underlying disease.

In the event of a suspected observation or device problem, a field technician will be dispatched to the site to resolve the problem. If the field engineer cannot resolve the problem, the device may be returned to Hologic/Plexus for analysis.

